1. INTRODUCTION

This document outlines the proposed analyses for the NEED-PT study. Briefly, NEED-PT is a physician-randomized (i.e., physicians serve as clustering or randomization units) trial evaluating efficacy of an embedded emergency department (ED) physical therapist in comparison to usual care. Individual ED patients will be consented and enrolled during their index ED visit and will follow the randomization assignment of their treating physicians. The primary outcome data will be analyzed at three months after the index ED visit, with additional data collection up to 12 months for evaluation of longer-term effects and exploratory endpoints.

Study Aims

The overarching study aims are as follows. **This SAP will focus on the details for Aim 2 analyses, which will guide the reporting of the primary study findings.** We reserve details of analyses surrounding additional aims for separate document(s):

Aim 1: Develop and field-test the Northwestern “Embedded” ED Physical Therapy (NEED-PT) intervention protocol for the routine co-evaluation of all ED patients with acute low back pain.

We will co-locate the ED physical therapist with the ED physician as part of the primary treatment team in order to remove biases in treatment selection and allow for earlier integration of ED-PT into patient care. A formalized protocol will enhance intervention fidelity in Aim 2 and facilitate dissemination of our care model.

Aim 2: Conduct a single-center, physician-randomized trial (n=40) comparing NEED-PT to usual care among ED patients (n=360) with acute low back pain to evaluate a primary outcome of pain-related functioning at three months and a secondary outcome of opioid use at three months.

H1: Patients receiving NEED-PT will report greater improvement in pain-related functioning compared to patients receiving usual care, as measured by average PROMIS Pain-Interference score

H2: Patients receiving NEED-PT will use fewer daily opioids on average.

Aim 3: Compare rates of diagnostic imaging utilization for ED visits with low back pain among ED physicians randomized to NEED-PT versus usual care.

H1: ED physicians randomized to NEED-PT will have a lower rate of diagnostic imaging utilization for low back pain compared to ED physicians randomized to usual care.

For patients enrolled in the study, study time points include baseline assessment (completed at the index ED visit), Week 1, Month 1, Month 2, Month 3 (primary endpoint), Month 6, and Month 12.

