6. STATISTICAL METHODS

We plan to use descriptive statistics to summarize baseline patient and physician-level variables both overall and by arm. We will use mean±standard deviation (or median and interquartile range [IQR] as appropriate) for continuous variables and frequency / percentage for categorical variables. Specifically, we will summarize age, sex, Keele STarT score, baseline patient-reported outcome scores (PROMIS-PI and ODI), analgesic medication prescription at ED discharge, and the variables listed above. Analyses will involve normal theory methods in general, and in cases of violations of assumptions, we will consider transformation and / or nonparametric / exact methods as appropriate.

Analyses will assume a two-sided 5% significance level. All primary efficacy and safety analyses will be pre-specified as outlined in this SAP, and deviations from planned analyses or post hoc analyses will be labeled as such in any reports or dissemination materials. We do not plan to control for multiple hypothesis tests.

In analyses for each outcome, we plan to control for the respective outcome value at baseline (i.e., in an analysis of covariance [ANCOVA] approach). Analyses for the primary outcome (Y) will involve a linear mixed model (LMM) with repeated measures with fixed effects for: study arm, baseline outcome score (Y0), timepoint, timepoint-by-arm interaction, and known influential predictor effects (age, sex, Keele STarT score). Inference will focus on treatment impacts for the outcome at three months. We will include a random physician effect to account for both within and between physician variability and also to allow for estimation of the intra-cluster correlation coefficient (ICC). The repeated measures on the same participant over time will also introduce a correlation structure across time points, providing the justification for modeling the correlation structure at the

participant level over time. We will use an unstructured correlation matrix to account for the repeated measures within a participant as this has the least assumptions. If the model does not converge or parameters cannot be estimated under this unstructured covariance pattern, we will explore simpler covariance patterns using residual estimated maximum likelihood (REML) comparisons. Including repeated measures per participant will allow us to make most use of all participant data after baseline. We will use assume an unstructured covariance across time.

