To evaluate efficacy, the Wald model type III test for fixed arm effect will be evaluated assuming a two-sided 5% type I error rate. The primary contrast of interest to address the primary research aims involves the comparison of the model-estimated mean outcome score at three months (T4) across study arms. This modeling strategy is robust to unbalanced (i.e., incomplete) data across study time points. We will also provide results for unadjusted analyses (i.e., without accounting for the pre-specified covariates). Analyses of additional outcomes will follow the same general analytic strategy: LMM with fixed arm, baseline outcome value, influential baseline covariate effects, and a random physician effect and covariance patterns to account for repeated measures within participants. We chose to incorporate baseline outcome as a covariate in the model, rather than as a time point, based on clinical reasoning. As these baseline values (e.g., PROMIS-PI score at the index ED visit) are assessed pre-intervention and primary analyses aim to assess outcome(s) as follow-up accounting for pre-intervention state. Incorporating this baseline value in the analytic model as a fixed effect will increase precision and reduce bias on the intervention effect estimate for primary outcome at the time point of interest as the baseline value will likely be highly correlated with outcome at follow-up (previous data: $p < 0.001$ for both PROMIS and ODI).

Residual diagnostics will assess model fit and assumptions, and in the case of violation, we will explore transformations / nonparametric methods as indicated above. In the event of poor model fit, we may explore different distributional assumptions as appropriate (e.g., Poisson for count or rate data) with the corresponding canonical link (e.g., log) function. As above, we will assess model fit via residual diagnostics and may consider transforming or nonparametric methods as needed.

Analyses for outcomes that are either binary or count will follow the same general approach as above; however, they will involve generalized linear mixed effects (GLMMs) models with the appropriate distributional (e.g., binomial or Poisson) and link (e.g., logit or log) assumptions. Modeling the covariance structure for these outcomes may result in unstable model estimates. If this occurs, we anticipate removing the random physician effect and including a random participant effect instead to account for correlation.

Exploratory Analyses

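### The primary mixed model fits one baseline slope to every follow-up visit; a baseline-by-timepoint term would protect the month-3 contrast at almost no cost

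*SAP*

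**What the plan says.** SAP section 6 specifies a repeated-measures linear mixed model with fixed effects for "study arm, baseline outcome score (Y0), timepoint, timepoint-by-arm interaction, and known influential predictor effects (age, sex, Keele STarT score". Baseline appears once, as a main effect. No other section adds a baseline-by-timepoint term.

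Section 1 lists the follow-up visits as "Week 1, Month 1, Month 2, Month 3 (primary endpoint), Month 6, and Month 12". Section 6 does not list the visits that enter the primary model. It does say that "Including repeated measures per participant will allow us to make most use of all participant data after baseline", which implies all six.

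The primary contrast is the "comparison of the model-estimated mean outcome score at three months (T4) across study arms". The reason given for the baseline covariate is that "Incorporating this baseline value in the analytic model as a fixed effect will increase precision and reduce bias on the intervention effect estimate" for the primary outcome at that time point. For the within-participant covariance the plan says "We will use an unstructured correlation matrix to account for the repeated measures within a participant as this has the least assumptions".

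Section 8 gives the only baseline correlation in the document: about 0.50 between baseline and month 3.

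**The concern.** The plan avoids assumptions in the covariance but keeps one in the mean model: that a one-point difference in the ED score predicts the same difference at Week 1 as at Month 12. In acute low back pain that association may well fade.

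If it does, the model estimates a weighted average of the visit-specific slopes. With similar SDs at each visit, the early visits have the smaller residual variances and so draw the average upward. The month-3 contrast is then adjusted with a slope that is not the month-3 slope, and part of any baseline difference between arms is left in the primary estimate. The remedies for poor fit in section 6 are transformations, nonparametric methods and other distributions. None of them would add the missing term.

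Some baseline difference is to be expected. Physicians are randomized, patients take their physician's arm, and the constrained randomization in section 5 balances physician characteristics rather than patients' PROMIS-PI scores.

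**Working it through.** **1. The plan's own figure.** Inputs from section 8: difference 3.5, SD 10, ICC 0.10, 16 physicians per arm with 7 participants each (112 per arm), baseline correlation 0.50, two-sided 5%.

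- Design effect: 1 + 6 × 0.10 = 1.6.
- Correlation of cluster means, with the cluster autocorrelation taken as 1 (not stated in the SAP): (7 × 0.10 + 0.90 × 0.50)/1.6 = 0.719.
- SE: 10 × √[(2/112) × 1.6 × (1 − 0.719²)] = 1.175.
- Power: Φ(3.5/1.175 − 1.96) = 84.6%, against 84% stated.

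This reproduces the plan's figure. It uses only baseline and month 3, so the present point does not alter it.

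**2. What the common slope does.** With complete data and separate arm means at each visit, the month-3 estimate is Dy3 − b × Dx. Dy3 and Dx are the between-arm differences in mean month-3 and baseline scores, and b is the fitted slope. With visit-specific slopes b is b3, the month-3 slope. With a common slope it is the generalized least squares average b = (1′S⁻¹r)/(1′S⁻¹1). Here r holds the six baseline-to-visit correlations, R the correlations among follow-up visits, and S = R − rr′. All SDs are assumed equal, so correlations and slopes coincide. The resulting shift is (b3 − b) × Dx, and month-3 residual variance rises by the fraction (b − b3)²/(1 − b3²).

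**3. Results with b3 fixed at 0.50.** The other correlations are assumptions. AR means a constant ratio per visit step.

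| Baseline correlations, Week 1 to Month 12 | Between-visit correlation | b | Shift per 2-point imbalance (size) | Month-3 residual variance |
|---|---|---|---|---|
| .50 throughout | any | 0.50 | 0 | 0 |
| .60 .57 .53 .50 .45 .40 | AR 0.7-0.8 | 0.52 | 0.03-0.04 | under +0.1% |
| same | exchangeable 0.5-0.7 | 0.54-0.56 | 0.08-0.12 | +0.2% to +0.5% |
| .70 .60 .55 .50 .40 .30 | AR 0.7-0.8 | 0.56-0.58 | 0.12-0.15 | +0.5% to +0.8% |
| same | exchangeable 0.5-0.7 | 0.64-0.77 | 0.28-0.54 | +2.6% to +9.8% |

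The last row at its upper end: b − b3 = 0.271, 2 × 0.271 = 0.54 points, and 0.271²/0.75 = 9.8%.

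**4. How large an imbalance to expect.** At design size Var(Dx) = 100 × (2/112) × 1.6 = 2.86, an SD of 1.69 points, taking baseline SD 10 and ICC 0.10. A 2-point chance difference is therefore ordinary.

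**5. Simulation.** Settings: true effect 3.5, clustered data, unstructured covariance, fitted without the physician effect, 200-400 runs per setting, Monte Carlo error about 0.06. Mild decay is .60 to .40. Marked decay is .75 to .25, steeper than any row above.

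| Setting | Common slope: mild / marked | Visit-specific slopes: mild / marked |
|---|---|---|
| Balanced baselines | 3.46 / 3.45 | 3.46 / 3.50 |
| 3-point baseline difference | 3.37 / 2.62 | 3.51 / 3.49 |
| About 19% missing at month 3, baseline-related dropout in opposite directions by arm | 3.76 / 4.07 | 3.59 / 3.58 |

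With the same dropout pattern in both arms the two models did not differ materially. The SD of the estimate with balanced baselines was 1.134 against 1.130 (mild) and 1.248 against 1.137 (marked), common slope first.

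**6. Cost of the extra term if slopes are in fact equal.** Estimating the month-3 slope alone from 224 participants has variance about 75/(224 × 100) = 0.00335. Multiplied by Var(Dx) = 2.86 this adds 0.0096 to a contrast variance of 1.175² = 1.381, or 0.7%. This is an upper bound, because the common slope must also be estimated. The simulated SDs were 1.095 and 1.094.

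**The case against.** A common baseline slope is a legitimate specification and contradicts nothing else in the SAP. The document neither supports nor refutes equal slopes, since it gives one correlation at one visit. With balanced baselines the month-3 estimate is on target even under marked decay. Under mild decay the precision gain is about as small as the cost of the term. All of this stands, and it limits the point to a cheap safeguard.

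The size also depends on the SDs. A slope is the correlation multiplied by the ratio of the visit SD to the baseline SD, so rising follow-up SDs would offset part of the decay. If residual variances were equal across visits, with exchangeable residual correlation, the common slope would be the plain mean of the six slopes. For the steeper path that is 3.05/6 = 0.508, almost exactly the month-3 value. The ranges above hold under equal total SDs and should be read that way.

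It can be said that imbalance is especially likely because arms are known at consent. The SAP says only that patients follow their physician's assignment, not who knows the arm at that moment, so only chance imbalance can be sized.

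Finally, an unstructured covariance plus a physician effect may already strain convergence, and section 6 plans a fallback for this. The proposed term adds fixed effects only and leaves the covariance unchanged.

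**Conclusion.** The point holds as a minor specification improvement. As written, one baseline slope serves all the visits the model uses, while the primary answer concerns month 3 alone. Under the stated assumptions the effect on the contrast runs from nil (equal slopes), through 0.03-0.12 points (mild decay), to 0.12-0.54 points (steeper decay) per 2-point baseline imbalance, against a target difference of 3.5. The direction depends on which arm has the higher baseline.

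Three stronger readings are not supported:

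- A reader might infer that the primary estimate is biased. Bias needs unequal slopes together with baseline imbalance or arm-differential, baseline-related dropout, and the SAP establishes none of these.
- A reader might infer that the SAP considered visit-specific slopes and rejected them. Its rationale concerns a different choice: baseline as a covariate rather than as an outcome time point.
- A reader might infer that the 84% power figure is wrong on this account. It does not involve the other visits.

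**What to change.** Add a baseline-score-by-timepoint interaction to the primary linear mixed model and keep the month-3 arm contrast as the primary estimate. Alternatively, state why a common slope is justified. Name the visits that enter the model in the same edit.

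The cost is five fixed-effect parameters and, if slopes are in fact equal, at most about 0.7% in variance. The estimand and test are unchanged. Version 2.0 was issued ahead of an anticipated lock on 7/25/25, and section 9 provides for documented revisions, so the change should be recorded before lock. A STarT-by-timepoint term is optional; nothing calculated here shows a need for it.

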8. POWER AND SAMPLE SIZE CONSIDERATIONS

Power calculations focus on the primary endpoint of PROMIS-PI at three months, and we desire adequate (at least 80%) power to detect the minimum clinically important PROMIS-PI score difference of 3.5-5.5 points as previous literature suggests (8). If we assume a standard deviation of 10 points, which is the defined standard deviation of PROMIS-PI, this corresponds to a desired minimal detectable effect size of $d=0.35$ standard deviation unit difference across arms. Power considerations also account for a 20% drop-out rate for physician clusters (e.g., physician leaves the practice or refuses participation after randomization) and a 20% lost to follow-up rate among recruited participants. We used “The Shiny CRT Calculator” to explore varying assumptions on cluster size (i.e., average number of participants per physician), number of clusters/physicians, and ICC. Under the parallel-arm, “cohort” design, with baseline measurement of primary outcome (PROMIS), the calculator also allows for an assumption on correlation between baseline and follow-up. The table below illustrates power to detect at least a 3.5 mean difference across study arms if we assume just two time points (baseline and three months, which we deem conservative as we will have up to seven time points of observation, including baseline) per participant with a correlation between the two of approximately 0.50. We conservatively estimate that we will need to enroll up to 360 total participants to account for worst-case (20%) scenario dropout for both physicians and participants. **Thus, after accounting for physician and participant dropout, a final sample size of 16 physicians per arm and 7 participants per physician (n=224 total or 112 per arm) achieves 84% power** to detect a mean between-arm difference of 3.5 PROMIS-PI points assuming standard deviation of 10 points, ICC of 0.10, and a two-sided 5% level of significance. In our pilot work, we found a small ICC (0.01-0.04), indicating minimal within-physician effects that were not significant; however, we utilize a more conservative estimate of the ICC at 0.10 in the event that greater than anticipated within-physician effects are encountered. In the event that ICC is lower than expected or dropout rate is lower than 20%, we anticipate often over 90% to detect a meaningful difference across arms. Similar effect size in secondary outcomes (e.g., 0.35 standard deviation units difference in ODI across arms) are also detectable with at least 80% power under similar assumptions. Additionally, we plan to conduct secondary longitudinal analyses involving multiple time points per participant (i.e., more data observations) using likelihood-based methods that are robust to missing data. Therefore, we anticipate adequate power to evaluate differences across arms in outcome trajectories. **Since our target final analytic sample size is 224 total participants, if we can reach our target with fewer participants enrolled than 360, we will consider stopping enrollment.** We will plan to monitor dropout rates, ICC, standard deviation, and within-participant correlation

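### The test the SAP names for efficacy, the type III arm test, averages over all follow-up visits; the primary endpoint and the power calculation are for Month 3

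*SAP*

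**What the plan says.** Section 6 of the SAP gives the primary model as a linear mixed model whose fixed effects include "study arm, baseline outcome score (Y0), timepoint, timepoint-by-arm interaction", plus age, sex and the Keele STarT score. It uses all post-baseline data, and the baseline score is a covariate rather than a time point. Section 1 lists the follow-up visits: "Week 1, Month 1, Month 2, Month 3 (primary endpoint), Month 6, and Month 12". Timepoint therefore has six levels.

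On the target of inference the SAP is consistent. Section 6 says "Inference will focus on treatment impacts for the outcome at three months". Section 8 says "Power calculations focus on the primary endpoint of PROMIS-PI at three months" and treats the all-visit work as secondary: "Additionally, we plan to conduct secondary longitudinal analyses involving multiple time points per participant".

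On the test, section 6 says: "To evaluate efficacy, the Wald model type III test for fixed arm effect will be evaluated assuming a two-sided 5% type I error rate". The next sentence reads "The primary contrast of interest to address the primary research aims involves the comparison of the model-estimated mean outcome score at three months (T4"), compared across arms. It attaches no test to that contrast and does not say how it relates to the type III test just named.

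**The concern.** In a model with an arm-by-timepoint interaction, the arm main effect and the arm difference at one visit are different hypotheses. The conventional type III test of arm (SAS, or sum-to-zero coding) asks whether the unweighted mean of the visit-specific differences is zero. The Month 3 question needs a specific contrast: the arm effect plus the interaction term for that visit.

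Followed literally, the efficacy sentence yields a primary p-value for an average from Week 1 to Month 12. That p-value can be significant when Month 3 is not, or the reverse, depending on how the effect changes over time. Once results are known, the efficacy sentence would support reporting one p-value and the primary-contrast sentence the other. Closing off that choice in advance is a main purpose of an analysis plan.

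**Working it through.** **1. What the type III arm test tests.** Write d1,…,d6 for the arm differences at the six visits. Under sum-to-zero coding the arm effect is (d1+…+d6)/6. Two numerical checks agree:

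- In simulated two-arm, six-visit data with unequal visit counts (fixed-effects fit), the sum-coded arm contrast was −1.546, equal to the unweighted mean of the six visit differences. The Month 3 difference in the same data was −0.263.
- With a true effect of 3.5 at Month 3 only, the sum-coded arm effect was 0.583, as expected from 3.5/6. With Week 1 as reference level the arm coefficient was 0.01. With Month 3 as reference it was 3.49.

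**2. Reproducing the stated power.** Inputs from SAP section 8: 16 physicians per arm, 7 participants each, SD 10, ICC 0.10, baseline-to-follow-up correlation 0.50, difference 3.5, two-sided 5%. One assumption is added, since the SAP does not state it: cluster autocorrelation 1.

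- Variance of a cluster mean: 100 × (1 + 6 × 0.10)/7 = 22.857.
- Correlation of cluster means between baseline and follow-up: R = (7 × 0.10 × 1 + 0.90 × 0.50)/1.6 = 0.719.
- SE of the Month 3 difference: √[(2 × 22.857/16) × (1 − 0.719²)] = 1.175.
- Power: Φ(3.5/1.175 − 1.96) = 84.6%, against the stated 84%.

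The same method reproduces all 45 cells of the power table to within 0.9 percentage points. The published power is therefore that of the Month 3 contrast.

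**3. The averaged test.** Assumptions outside the SAP: the same SE at all six visits, and a correlation ρ of 0.3 to 0.7 between visit-specific differences. Then SE = 1.175 × √[(1 + 5ρ)/6] = 0.759, 0.898 and 1.018 for ρ = 0.3, 0.5 and 0.7. The rejection rate is Φ(mean/SE − 1.96) + Φ(−mean/SE − 1.96).

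| Assumed effect at Week 1, Months 1, 2, 3, 6, 12 | Mean | Averaged test, ρ = 0.3 / 0.5 / 0.7 | Month 3 contrast |
|---|---|---|---|
| Constant: 3.5 throughout | 3.5 | 99.6 / 97.4 / 93.0% | 84.6% |
| Sustained late: 0, 0.5, 2, 3.5, 3.5, 3.5 | 13/6 = 2.17 | 81.5 / 67.5 / 56.7% | 84.6% |
| Peak and fade: 0.5, 1.5, 2.5, 3.5, 1.5, 0.5 | 10/6 = 1.67 | 59.4 / 45.9 / 37.4% | 84.6% |
| Early only: 4, 4, 2, 0, 0, 0 | 10/6 = 1.67 | 59.4 / 45.9 / 37.4% | 5% |

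If the correlation structure of step 2 is carried exchangeably to every visit, the baseline-adjusted correlation is R/(1+R) = 0.719/1.719 = 0.42. That lies inside the range used and gives SE 0.844.

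**4. If the model stopped at Month 3.** The arm test would average four visits, with SE = 1.175 × √[(1 + 3ρ)/4] = 0.810 to 1.035. The peak-and-fade mean becomes 8/4 = 2.0, with rejection 69.5% to 48.9%. The early-only mean becomes 10/4 = 2.5, with rejection 87.0% to 67.6% and still no Month 3 difference.

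**The case against.** The strongest reply is that the intended test can be recovered. The sentence after the efficacy sentence names the Month 3 contrast, section 6 sets a general two-sided 5% level, and sections 1, 2 and 8 all point to Month 3. Section 8 also ranks multi-timepoint analyses as secondary, so presenting the all-visit average as the primary result would cut against most of the document. This stands as far as the estimand goes: Month 3 is clear. It does not settle the test. The general 5% level covers every analysis, and the only sentence that assigns the efficacy decision assigns it to the arm effect.

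Second, the meaning of the arm test depends on coding, and section 9 allows R as well as SAS. That is correct. Under R's default reference coding the arm term can refer to the reference visit, Week 1 in the check above. It equals the Month 3 difference only if Month 3 is set as reference, which the SAP does not say. This adds a further possible reading and does not remove the mismatch.

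Third, the SAP does not list the visits entering the model. Six is inferred from the visit schedule and the stated use of all post-baseline data. A four-visit model changes the figures but leaves the mismatch, as step 4 shows.

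Fourth, the effect profiles are illustrations, and under a constant effect the averaged test is the more powerful one. Both are true. The figures show that the two tests can diverge in either direction; they do not show a systematic loss of power.

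**Conclusion.** The concern holds. The sentence that assigns the efficacy test names one that, in the specified model and under conventional type III coding, does not test the primary endpoint. The 84% power figure is sound and applies to the Month 3 contrast. Among the illustrative profiles with 3.5 points at Month 3, the averaged test's power runs from 37% to over 99%. With an early-only effect it rejects 37–59% of the time although the Month 3 difference is zero.

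These rates rest on six visits in the model, equal SE at each visit, correlation 0.3–0.7 between visit differences, cluster autocorrelation 1 and the assumed profiles. The mismatch itself needs only the interaction term and the conventional meaning of the test. Because it concerns which p-value carries the primary claim, it should be corrected before the analysis is run.

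**What to change.** Replace the efficacy sentence in section 6 with wording such as: *The sole primary efficacy test is the two-sided 5% Wald test of the between-arm difference in model-estimated mean PROMIS-PI at Month 3 from the linear mixed model. The overall type III arm test and the arm-by-timepoint test are supportive.*

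The cost is a change of SAP wording, for which section 9 already provides version control. Model, endpoint, data and sample size are unchanged, and one LSMEANS or ESTIMATE statement (or an emmeans contrast in R) gives the result.

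Two optional clarifications could go into the same edit, though the finding does not depend on them: state that the models for additional outcomes also carry timepoint and arm-by-timepoint with the same Month 3 contrast, and name the degrees-of-freedom method (Kenward-Roger, for example).
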